### Experimental controls

In order to draw inferences regarding the necessity of a specific region of the brain and/or the timing of a particular type of stimulation for somatosensory perception, we require control conditions that match our experimental conditions in terms of the sensations and parameters related to stimulation, but that are different in the variable of interest (e.g., the locus and/or timing of stimulation). In this study, we will incorporate two different types of controls.

- (1) **Within-session 'no stimulation' trials.** During the TMS-EEG sessions, we will collect trials in which TMS pulses are applied, and trials with no TMS pulses, during the tactile detection task. During all trials, the TMS coil will be held over the participant's head as directed by the neuronavigation system, but on "no stimulation" trials, no trigger will be sent from the task code to the stimulator. In the place of a TMS pulse(s), a noise will be played that sounds like the clicking noises made by the stimulator.
- (2) **Between session region of interest "active" control.** Active stimulation control refers to the active stimulation of a region of the brain that is not hypothesized to be necessary for the cognitive control process under study and/or stimulation with a pulse timing that is hypothesized to not affect the process of interest. As active stimulation control involves active TMS stimulation, it will employ identical procedures and protocols to those described below for experimental stimulation conditions. We ask participants to take part in two different TMS-EEG sessions on different days, separated by at least one week. In one session, we will apply TMS pulses over our region of interest in somatosensory cortex. In a second session, we will apply TMS pulses over a control region of interest.

## Locus of Stimulation

For the experiments in this protocol, we will stimulate focal regions of neocortex mainly in the frontal (motor cortex) and parietal lobes. Specific target regions are those that are hypothesized to support somatosensory perception and will be stimulated in order to test for a change in observed outcome measures. Active stimulation control regions that are not hypothesized to be necessary for a particular aspect of somatosensory perception under study will be selected in order to provide an active stimulation control against which the target stimulation condition can be compared. In cases where the participant's own brain image is used for localization, this will have been collected during a prior MRI session.

## TMS Devices

Several devices are used during a TMS experiment, including stimulators, coils, and navigation devices. Below, we briefly describe each device and its purpose. A subset of these devices would be used for each TMS session depending on the specific stimulation protocol and experiment. We indicate these uses in the descriptions below.

Magstim Super Rapid Plus. This stimulator device is used for delivery of repetitive trains of TMS with pulses at high frequency and intensity. The Super Rapid Plus device can produce rTMS at 10 Hz at 100% power and theta burst stimulation at ~60% power.

Magstim Bistim^2. The Bistim^2 stimulator system couples two Magstim 2002 stimulators for power output needed to conduct single-pulse, paired-pulse and dual-pulse stimulation protocols. The paired-pulse method delivers two TMS pulses through a single coil at variable (programmable) intervals.

Magstim Double Rapid Air Film Coil: This 70 mm diameter "Figure 8" coil is specially designed for rTMS work. Coils used for rTMS require active cooling mechanisms to prevent coil overheating. This coil is air-cooled.

Magstim D702 coil. This butterfly shaped (Figure 8) coil is designed to deliver high-power single-pulse in a narrower field, to activate or suppress a more focal area than is possible with other flat coils. This coil will be used for most single-pulse and paired-pulse work. It could also be used for dual-pulse.

Magstim 50 mm butterfly coil. This coil is designed to deliver more focal stimuli than the D702 coil, though at lower possible peak powers due to its smaller diameter. Used in projects requiring the most focal stimulation possible and for dual-pulse experiments requiring coil placement in close proximity.

Magstim Double Rapid Air Film SHAM coil. This 'sham' coil will have a form factor identical to the Double Rapid Air Film Coil, but without functionality to deliver TMS. The coil will be used for mock-TMS, an important control procedure particularly for research studies employing blinded design.

Magstim D702 SHAM coil. This 'sham' coil will have a form factor identical to the D702 coil, but without functionality. As with the other sham coil, we will use this non-functional coil for experimental control purposes.

Rogue Research Brainsight Stereotaxic Navigation System. This system is used to precisely position TMS coils for stimulation of specific anatomical targets. The system has continuous feedback and plots the presumed brain location and orientation of the TMS pulse trial-by-trial. Neuronavigation interface with TMS is critical given the inherent limitation of using superficial anatomical landmarks and head measurement for establishing target coordinates.

Rogue Research Brainsight Trigger module. This device interfaces with the brain stimulation equipment to permit acquisition of the estimated stimulation site for each TMS pulse or repetitive bout.

Magstim EMG Interface Module. This module allows for control of TMS pulse delivery and delay of the TMS capacitor recharge from a remote PC. It also provides output triggers e.g. to time-lock TMS pulse delivery with the Brainsight Stereotaxic Navigation System and the actiChamp Plus EEG System.

## TMS Stimulation Protocols

We will use the following stimulation protocols across experiments. Only one protocol will be used for any given experimental session, in addition to motor thresholding (see EMG Procedures). Following the protocol descriptions, a summary of stimulation parameters are provided in Table 1. These parameters include the intensity of stimulator output, expressed as a percent of active motor threshold (% MT; see EMG Procedures), the within-train frequency of stimulation (Hz) (i.e., how often per second pulses are delivered in a continuous train), the number of pulses per train or trial, and the inter-train/trial interval (msec.) (i.e., the minimum time separating two trains of pulses, or trials with single pulses).

As detailed in the “Risks and Benefits, TMS” section, TMS is considered low risk when protocols use stimulation parameters within established international safety norms. Parameters and procedures for all protocols cited here are based upon published international consensus safety guidelines (Rossi et al., 2009). In Figures 1 and 2, we have provided the relevant tables from the international consensus safety guidelines published in (Rossi et al., 2009).

Mkon,

#### *Single pulse TMS to primary motor cortex, somatosensory cortex, or a control region of interest*

Delivery of single TMS pulses (< 1 Hz) over motor cortex will primarily be used to assess cortical excitability. The elicited response in EMG of the fingers, hand, or arm will be recorded (see EMG Procedures). These data are conventionally used to calibrate stimulator output intensity, which is known as “motor thresholding”.

Single TMS pulses to motor cortex, somatosensory cortex, or a control region of interest can also be used to characterize local changes in excitability due to experimental manipulations.

The time between single TMS pulses will be irregular, but they will always be delivered at least 3 seconds apart. See Figure 1 for relevant safety guideline.

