##### Tactile Stimulation

This device is designed to apply light, brief, non-painful and non-damaging taps to the skin. The participant's hand will rest on a solid plastic frame through which tactile stimuli will be delivered via a plastic contactor (similar to a small plastic screw). Stimuli (single cycle of a 100 Hz sine wave, 10 msec. duration) will be generated by fused multilayer piezoelectric benders, and will be applied to the distal pads of the third digit via a Delrin plastic contactor affixed to a piezoelectric bender (7 mm diameter presented within a 1 cm circular rigid surround). The device will not be glued to the skin. Stimulus onset and intensity will be computer-controlled using customized software.

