## TMS

During the TMS-EEG study sessions, participants will receive single or triple pulses of TMS over somatosensory cortex or a control location (parietal, temporal or visual cortex) during the tactile detection task, and concurrent with EEG recording. This will allow us to examine the brain response to TMS with high temporal resolution.

TMS is a method for electromagnetically inducing a weak, transient electric field in the human brain. TMS works by passing a brief, powerful current of electricity through a small coil of wire placed near the head. The pulsing of this current through the coil produces a transient magnetic field directly below the coil. Importantly, this magnetic field harmlessly passes through hair, scalp, and skull and induces a brief, weak electrical current in the brain that transiently depolarizes neurons focally underlying the coil. The change in neural activity for this single pulse is very brief (around 1/10 of a second or less) and occurs at a shallow depth (e.g., approximately 1.5 to 2.0 cm below the scalp), depending on the coil geometry and stimulator output intensity.

Participants in TMS experiments sit in a custom chair. They may be reclined in the chair during stimulation or they may sit upright with their head held unrestrained. A coil is placed on the participant's head in various positions and may be held by an experimenter or by a guidance arm. The positioning of the coil on the head may either be determined using head landmarks or an MRI-guided region-of-interest targeting "neuronavigation" system.

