## EMG & Motor Thresholding

Electromyography (EMG) is used to accurately and precisely measure electrical potentials in the muscles. Recording electrodes are taped/stuck (if they have a sticker backing) to the skin above a muscle of interest following a brief cleaning of the area using an alcohol wipe. An amplifier is used to amplify small, recorded muscle potential signals. This set up can be used to measure the latency and amplitude ( $\mu\text{V}$ ) of Motor Evoked Potentials (MEPs) in the muscles produced by TMS over the contralateral motor cortex.

The quantified amplitudes of MEPs evoked by TMS are conventionally used to determine motor thresholds for calibration of stimulator output strength across different types of TMS protocols. In this study, the proposed TMS protocols will utilize stimulator output strengths measured as a function of active motor thresholds, as indicated in Table I.

To determine an individual participant's active motor threshold (AMT), we will apply single pulses of TMS to primary motor cortex. AMT is defined as the minimum stimulator intensity needed to elicit a  $100\ \mu\text{V}$  or greater EMG response in a target muscle in 50% of pulses (e.g., 5/10) applied to the contralateral primary motor cortex when the target muscle is voluntarily contracted using 10% of maximum voluntary force.

AMT will be determined by initializing the stimulator's output to a proportion of its maximum output that is expected to yield a 50% probability of eliciting an EMG of the criterion intensity ( $50\ \mu\text{V}$  for resting MT, or  $100\ \mu\text{V}$  for active MT). The intensity of stimulation will then be adjusted incrementally to as much as 100% of stimulator output until the AMT is achieved. The TMS pulses used in this procedure will be delivered no faster than 1 pulse every 5 sec (.2 Hz). This slow rate is well within established safety limits (see Figure 1).

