If our highest motor threshold (120% active motor threshold) corresponded to 100% stimulator output, the participant's active motor threshold would be  $\sim 83$ . This is highly unlikely in TMS studies without EEG. However, in studies in which the coil is placed further from the scalp due to large active electrodes, motor thresholds increase due to a quick dropoff in magnetic field strength with distance. Therefore, we will cap the maximum motor threshold at 76. If a participant does not have a motor threshold  $\leq 76$ , they will be paid for a full TMS-EEG session, but then excluded from the study and allowed to leave after the motor thresholding procedure.

**THE BLUE TEXT IN THE FOLLOWING SECTIONS IS A GUIDE TO ENSURE ALL RELEVANT INFORMATION IS INCLUDED IN YOUR APPLICATION. YOU MAY DELETE THE BLUE TEXT BEFORE SUBMISSION**

**4. Participant Population.** *In order to approve research, the IRB must determine that the selection of participants is equitable and reasonably related to the purpose and aims of the research. The IRB must also consider whether adequate safeguards are in place to minimize any risks that are unique to vulnerable populations. To make this determination, the IRB must review all methods and materials used to contact and recruit potential participants, including letters, flyers, emails, etc.*

[figure not shown]
It is necessary to test human participants in this multi-modal study. We will link our EEG and perceptual outcomes to cellular and circuit mechanisms with our unique biophysically principled model of human somatosensory cortex (SI). Additionally, due to the complexity and highly folded nature of the human brain, TMS effects may not directly translate to other species; indeed, one goal of this proposed work is to understand the effects of TMS localized specifically to human SI in order to inform development of therapeutic TMS protocols for clinical human use. Finally, due to the relative size of the human brain in comparison with the TMS coil, TMS is capable of having a more localized and thus interpretable impact on somatosensory processing than if we were to use a smaller animal model.

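### Single pulses over SI may reach 120% of active motor threshold during the finger-tap task, but EMG is described only for motor-cortex pulses, so a possible evoked hand response could pass for SI inhibition

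*Protocol*

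**What the plan says.** Under the heading "Single pulse TMS to primary motor cortex, somatosensory cortex, or a control region of interest", the protocol puts three sites under one single-pulse protocol. Table I gives that protocol a ceiling of 120% of active motor threshold and does not separate the sites. EMG & Motor Thresholding treats that value as the top of the range in use: "If our highest motor threshold (120% active motor threshold) corresponded to 100% stimulator output".

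The TMS section places the pulses within the task: "participants will receive single or triple pulses of TMS over somatosensory cortex or a control location (parietal, temporal or visual cortex) during the tactile detection". Under Tactile Stimulation, "The participant's hand will rest on a solid plastic frame", and the taps "will be applied to the distal pads of the third digit via a Delrin plastic contactor". The section on perceptual tasks also allows taps to the foot.

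EMG appears in two places. The single-pulse section mentions it when describing motor-cortex pulses that assess excitability and calibrate output: "The elicited response in EMG of the fingers, hand, or arm will be recorded (see EMG Procedures"). EMG & Motor Thresholding says "This set up can be used to measure the latency and amplitude" of motor evoked potentials "produced by TMS over the contralateral motor cortex", as the basis for the threshold.

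Experimental controls describes two controls: no-pulse trials with a recorded click, and a second session over a control region. It asks that controls match the experimental condition in the sensations that stimulation causes.

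**The concern.** Aim 2 predicts that single pulses or bursts of three over SI will reduce tactile detection, depending on timing. The hand area of SI adjoins the hand area of motor cortex (standard anatomy, not stated in the protocol). An SI pulse strong enough to reach motor cortex could move the finger on the contactor, or create sensation in it, just when a barely perceptible tap is delivered.

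A tap missed for that reason would count as a non-detection on an SI-TMS trial, which is the pattern that Aim 2 predicts. Sensory feedback from the movement would also enter the EEG response that Aim 2 measures and Aim 3 models. Without EMG on task trials, the trial could neither show this happening nor rule it out. EMG not recorded in the session cannot be recovered by later analysis, so this is a matter for the protocol.

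**Working it through.** **The plan's own figure.** EMG & Motor Thresholding says that if 120% of active threshold were full stimulator output, the threshold would be about 83. Check: 100 / 1.20 = 83.3, which agrees. At the cap of 76, 120% is 1.20 × 76 = 91.2% of output, so the cap does not keep pulses below 120% of threshold.

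**Which pulses are exposed.**
- Single pulses: up to 120% of active threshold, and placed in the task by the TMS section. Exposed.
- Triplets: at most 90% in the triple-pulse section and at most 80% in Table I. These two figures must be reconciled, but both are below threshold. Not the concern here.
- Paired pulses: up to 100% in Table I, but the TMS section names only single and triple pulses for the task. Not the concern here.

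**How far above threshold a resting hand might be.** Active threshold is defined with the target muscle contracted at 10% of maximum force, whereas the task hand rests. Let r be the ratio of resting to active threshold. The documents do not give r; I assume 1.0 to 1.4. Then 120% of active threshold equals (120 / r)% of resting threshold:

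| r (assumed) | % of resting threshold |
|---|---|
| 1.0 | 120 |
| 1.1 | 109 |
| 1.2 | 100 |
| 1.3 | 92 |
| 1.4 | 86 |

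The range straddles 100%, and this is before allowing for the coil being aimed at SI instead of the motor hotspot. A hand response is therefore possible at the ceiling, but not assured.

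**What it would do to the contrasts.** Let p be baseline detection, q the share of SI-pulse trials with a hand response, and L the relative loss of detection on those trials. With no true SI effect:

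apparent drop against no-pulse trials = p × q × L

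If the control site evokes a response on a share c of its trials:

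apparent drop against the control site = p × (q − c) × L

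Assume p = 0.50 and L = 0.50 (neither is in the documents):
- q = 0.10: 0.50 × 0.10 × 0.50 = 2.5 points
- q = 0.25: 0.50 × 0.25 × 0.50 = 6.25 points
- q = 0.50: 0.50 × 0.50 × 0.50 = 12.5 points

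For a temporal or visual control site, c should be near zero, so the site contrast shows the same drop as the no-pulse contrast. For a parietal site, which the TMS section also allows, c might not be zero, and part of the artefact could cancel.

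**The case against.** A reader might infer that the hand is stimulated at 120% of its own motor threshold, that EMG is expressly restricted to motor-cortex pulses, and that no control could reveal the problem. The documents do not support that reading.

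- The 120% is a ceiling in a table of parameter ranges, on a row that also covers motor-cortex pulses. No section sets the SI task intensity at that value.
- The reference is the active threshold, found over motor cortex under contraction. The muscle is not fixed more closely than fingers, hand or arm.
- The protocol is silent on EMG in the task; it does not exclude it.
- A parietal control site might share some of the effect. Experimental controls also mentions pulse timing as a possible active control, although the session it describes changes only the region, and masking by a twitch would itself depend on timing.
- Staff watch participants while the tactile stimulator runs, so gross movement might be seen. That monitoring is for discomfort and malfunction, and no trial-level record is described.
- The sizes above come from assumed inputs. They show that the effect could matter, not that it does.

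There is also a fair objection to making response-free trials the main analysis. That would select on an event after the pulse, in TMS trials only and probably more often in the SI session. The protocol's own premise is that ongoing brain state predicts detection, so the trials kept could differ in the state under study.

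These points limit the claim and shape the remedy. They do not remove the gap: nothing in the protocol says that hand responses to SI task pulses will be measured.

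**Conclusion.** The concern holds as a design gap limited to single-pulse sessions with taps to the finger. The protocol permits SI pulses above active motor threshold during the task and describes no measurement that would detect a hand response to them. Neither the no-pulse trials nor a temporal or visual control site would reproduce such a response, so it could imitate the predicted result.

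Whether it occurs, and how often, cannot be told from the documents. The range of 2.5 to 12.5 points rests on assumed values for baseline detection, response rate and loss per response; a response rate near zero would make it negligible. This is not an error or a contradiction in the text. It is a worthwhile, inexpensive improvement, because it lets the trial test a rival explanation of its main causal claim.

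**What to change.** In the single-pulse section and in EMG & Motor Thresholding, state that:

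1. the thresholding electrodes stay on the hand that receives the taps, and EMG is recorded through the detection task in the single-pulse TMS sessions (III and IV);
2. an evoked response is flagged by an amplitude fixed in advance, for example the 50 microvolt resting criterion already in EMG & Motor Thresholding, and the rate of flagged trials is reported by stimulation site;
3. the main analysis keeps all trials, and the perceptual and EEG contrasts are repeated without flagged trials as a sensitivity analysis, with a note that this selects on a post-pulse response.

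Stimulation intensity is unchanged. Thresholding already accompanies the session protocol, so the electrodes and amplifier are in use. The cost is a somewhat longer EMG recording and one extra analysis.

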#### *Paired pulse TMS to somatosensory cortex or a control region of interest*

Delivery of paired pulses involve delivery of two pulses, whereby a single pulse is administered 5-500 ms prior to another pulse from the same coil over the same brain region or from another coil over a second brain region. Such paired pulse designs are useful for characterizing changes in the interactions of two neural regions. The time between pairs of pulses will be irregular, as they are determined by the timings of specific trial events that may not be spaced at regular intervals. However, these paired-pulse trains will be administered at least 5 secs apart ( $\leq 0.2$ Hz). Paired pulse stimulation has not been found to be associated with any increased risk relative to standard single pulse TMS (Rossi et al., 2009). See Figure 1 for relevant safety guideline.

#### *Tripe pulse TMS to somatosensory cortex or a control region of interest*

In this custom TMS protocol, we will deliver one set of three rapid biphasic TMS pulses (40-60 Hz “triplet”) per trial while the participant is engaged in a tactile detection task (“online”). The inter-pulse interval within a triplet will be  $\geq 15$  msec., and we will present one TMS pulse triplet per trial. We will design the trial structure of our task such that there is at least a 5 second inter-triplet interval (ITI) between trials. A maximum of 900 TMS pulses total (300 trials of 3 pulses per trial) will be presented during this protocol. Pulses will be delivered at  $\leq 90\%$  of active motor threshold.

This protocol is intended to mimic a single set of triplet pulses that, when continuously or intermittently presented, comprise the fundamental units of conventional cTBS. Although no clear international safety consensus guidelines exist for the protocol that we propose, we have conservatively extrapolated protocol parameters from existing studies that have been safely performed, as follows below.

In conventional Theta Burst Stimulation (cTBS) protocols (Huang et al., 2005), similar biphasic triplets of TMS pulses (50 Hz) are presented continuously for 40 seconds, with a 200 msec. ITI. The standard cTBS protocol for which international safety consensus has been reached involves 600 total pulses per session (200 triplets, 80% active motor threshold; See Figure 2 for relevant safety guideline), but 900 pulses have also reportedly been safely performed (Rossi et al., 2009). Therefore, we will not exceed 900 total pulses (300 trials of 3-pulse triplets) in a single session of triple pulse TMS, and will carry out no more than one session per day for an individual participant.

Quadripulse Stimulation (QPS; Hamada and Ugawa, 2010) is another established type of TMS pulse protocol in which 4 monophasic TMS pulses are presented rapidly, with inter-pulse intervals  $\geq 1.5$  msec. (typically ranging

01/21/2019

between 1.5-2.5 msec.). International safety consensus guidelines have been reached for 1440 total pulses (360 trials) of QPS with an inter-pulse interval between 1.5-1250 msec. at 90% of active motor threshold, given the quadripulse trains are delivered  $\geq$  every 5 seconds (Rossi et al., 2009; See Figure 2 for relevant safety guideline). Therefore, our protocol involves an ITI of at least 5 seconds.

